7.9.2.7 Supporting Analysis

Two sensitivity analyses may be performed.

If primary safety endpoint data are missing for more than 5% of cases in the FAS, multiple imputation (MI) will be used to impute the missing outcome data. The model variables used for the MI analysis may include but are not limited to study site, age, and gender. A summary of the variables included, and the related model selection process will be provided. The fully conditional specification method with 10 burn-in iterations and 10 repetitions (M=10) will be used for imputation if MI is utilized.

Another sensitivity analysis will be to evaluate the primary safety endpoint using the PPAS.

Three exploratory analyses are planned for this endpoint as well, wherein the rate of major complications within 30 days will be limited to just the related to device, related to procedure, and related to underlying condition. Relatedness in this exploratory analysis will be any rating other than "Not Related" or equivalent.

7.9.3 Secondary Objectives

Descriptive statistics will be used to summarize secondary endpoints. In addition, performance goals are pre-specified based on the Urology Clinical Data Analysis, as well as considerations of clinically meaningful margins and statistical confidences and 95% confidence intervals might be provided as appropriate.

The role of the secondary endpoints is to explore additional effects and outcomes associated with either the procedure or the disease state. The pre-specified performance goals serve as benchmarks for interpretation rather than thresholds for statistical significance of clinical trial success in this study.

Statistical evaluations for secondary objectives with performances goals are not powered in this study. Therefore, the secondary endpoints are planned to be analyzed descriptively with no plans for statistical testing.

7.9.3.1 Objectives, Endpoint Definitions and Derivations

Endpoint #	Objective	Endpoint Definition and Derivation
1	Overall Complication Rate	Rate of overall complications within 30 days is calculated as the proportion of subjects who experience any related (device, procedure, or underlying condition/disease) adverse event prior to or during the 30 calendar-days post-procedure. The AE start date collected with the adverse event will be used to determine whether a complication was experienced.
2	Operative Time	Operative time is defined as the difference in time in minutes between the procedure end time and the procedure start time. The procedure start time is the time of first incision and the end time is the time of skin closure.
3	Intraoperative Estimated Blood Loss	The estimated amount of blood loss is reported during the procedure in mL.
4	Transfusion Rate	Occurrence of a blood transfusion is captured as an adverse event. A blood transfusion is defined as an AE that resulted in any treatment and then a bleeding complication led to a blood transfusion and started prior to or during the 30 calendar-days post-procedure.
5	Device-related Conversion	A conversion is defined the same way as in Section 7.9.1.2 . A device related conversion is defined as a conversion where either the primary or any other reason for conversion is denoted as Adverse Event that is related to the device or procedure, Device Deficiency, Non-Subject Adverse Event, or Poor Visualization.

6	Hospital Length of Stay	
The length of hospital stay is the number of days that the subject was in the hospital from the start of the surgical procedure to hospital discharge. The number of days in the hospital can be found as the difference in minutes between the discharge date and time and the procedure date and time divided by 1440 min/hour, i.e.,
 $(Discharge Date and time - procedure date and time)/1440.$
7	Readmission Rate	A readmission in a subject is identified if a related (device, procedure, or underlying condition/disease) adverse event with a start date of or after the index procedure date and prior to or during the 30-calendar days post-procedure that resulted in the subject being hospitalized. Additionally, the hospital start date reported within the AE must be prior to or during the 30 calendar-days post-procedure and on or after the reported index procedure discharge date.
8	Reoperation Rate	Reoperation through 30 days is identified in a subject if they experience a related (device, procedure, or underlying condition/disease) adverse event that resulted in treatment with a surgical procedure and the AE start date was prior to or during the 30-calendar days post-procedure.
9	Mortality Rate	Death through 30 days is identified as an AE that led to death which occurs during the procedure or up to the 30 calendar-days post-procedure.
10	Device Deficiencies	A subject is identified as experiencing a device deficiency if a device deficiency occurred before, during, or after the subject's procedure.
11	Overall Survival	Subject death will be identified as an adverse event that leads to death where the adverse event start date is on or after the procedure date or if the subject is noted by the site to have died during follow-up. Time to death will be calculated as the difference in days between death and the procedure date.
12	Progression-free Survival	Disease progression will be identified in a subject if their disease state is noted by the site, during follow-up, as "disease reoccurrence, disease progression", or if subject death had been noted. This is assessed as either at the time of the follow-up visit or at the time of last contact, whichever is earlier will be denoted as the time of disease

		progression. Time to disease progression is calculated as the difference in days between disease regression and the procedure date.
13	Disease-free Survival	Disease reoccurrence will be identified in a subject if the subject disease state is noted by the site, during follow-up, as “disease reoccurrence, disease progression”, “disease reoccurrence, disease stable”, or if subject death had been noted. This is assessed either at the time of a follow-up visit or at the time of last contact, whichever is earlier will be denoted as the time of disease reoccurrence. Time to disease reoccurrence will be calculated as the difference in days between disease reoccurrence date and the procedure date.

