5.1.4 Secondary Endpoints

Secondary objectives include descriptive analyses of secondary endpoints.

The following safety and performance data shall be collected through 30 days post-procedure to assess the overall safety and performance of the Medtronic Hugo™ RAS System when used for urologic RAS:

- Complication rate: Overall rate of subjects with one or more complications (Clavien-Dindo Grade I or higher), from the first incision through 30 days post-procedure
- Operative time
- Intraoperative estimated blood loss (mL)
- Transfusion rate
- Rate of device-related conversion
- Hospital length of stay
- Readmission rate (through 30 days)
- Reoperation rate (through 30 days)
- Mortality rate (through 30 days)
- Rate of device deficiencies

The following long-term secondary endpoints will be assessed through 5 years in oncologic subjects:

- Overall survival
- Progression-free survival
- Disease-free survival

Performance Goals for Secondary Endpoints

The details are summarized in the table found in **Section 14.5**.

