12.1 Adverse Events

All Adverse Events (AEs) will be collected, starting from the time the informed consent form is signed through 30 days (+7) after the day of the procedure regardless of their severity or relationship to the Hugo™ RAS or study procedures. After 30 days, AEs will be assessed by the surgeon and those AEs deemed attributable to the underlying surgical indication, procedure or surgical device will be reported. All deaths will be collected via AE regardless of relatedness. Reporting of these events to Medtronic will occur on an AE Form, including event description, date of AE, treatment, resolution, assessment of both the seriousness of the AE and the relatedness to the system components. Each AE must be recorded on a separate AE eCRF.

AE definitions used in this study are based on ISO 14155:2020 (Clinical Investigation of Medical Devices for Human Subjects -- Good Clinical Practice). Documented pre-existing conditions are not considered AEs unless the nature or severity of the condition has worsened. See **Section 14.1** for details regarding AE analyses in each study analysis set. In addition, AEs impacting users or other persons (non-subject AEs) will be collected on a non-subject AE CRF.

Any unresolved procedural or device-related events that are still ongoing past study exit will be monitored by the physician per their institutional standard-of-care.

Unavoidable adverse events (UAE) (those that are inherent to the procedure and are expected to occur in all subjects for an expected duration) listed in **Table 9** will not be captured or reported unless the adverse event worsens or persists outside the stated timeframe post procedure. **Section 11.1** includes a list of several, but not an all-encompassing anticipated adverse events.

All deaths, serious adverse events related to the Hugo™ RAS System and/or study procedures and Clavien-Dindo Grade III and IV complications will be adjudicated by an independent CEC.

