Relatedness	
System Related (Includes all components of the Hugo™ RAS System, associated introduction tools, operational and installed software and programmers as defined in the CIP)	An AE that results from the presence or performance of any component of the system. Device-related: An AE that results from the presence or performance (intended or otherwise) of the device. Refer to Section 7.1 . Investigational Feature: An AE that results from the presence or performance (intended or otherwise) of the Hugo™ RAS System.
Procedure Relatedness	An AE that occurs due to any procedure related to the Hugo™ RAS System.
Underlying Condition or Disease Relatedness	Underlying condition refers to a chronic disease or condition that a subject has prior to any acute treatment/surgery (like diabetes, heart disease, obesity, cancer, etc.).
Relatedness Classification (Procedure, underlying condition, or device)	Not related: relationship can be excluded when: 
the event has no temporal relationship with the use of the device or procedure;the event does not follow a known response pattern to the device (if the response pattern is previously known) and is biologically implausible;the discontinuation of device application or the reduction of the level of activation/exposure - when clinically feasible – and reintroduction of its use (or increase of the level of activation/exposure), do not impact on the event;

Medtronic Business Restricted

This document is electronically controlled

CONFIDENTIAL 056-F275 Rev E Clinical Investigation Plan Template

Medtronic Expand URO Clinical Investigation Plan

- the event involves a body-site or an organ not expected to be affected by the device or procedure;
- the event can be attributed to another cause (e.g., an underlying or concurrent illness/ clinical condition, an effect of another device, drug, treatment or other risk factors);
- the event does not depend on a false result given by the device used for diagnosis, when applicable;

In order to establish the non-relatedness, not all the criteria listed above might be met at the same time, depending on the type of device/procedures and the event.

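### SAP 7.9.3.1 counts only related adverse events for overall complications, readmission and reoperation; for overall complications this contradicts protocol 5.1.4 and SAP 4.2

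*SAP*

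**What the plan says.** **Overall complications (secondary endpoint 1).** Protocol 5.1.4 defines this as "Overall rate of subjects with one or more complications (Clavien-Dindo Grade I or higher), from the first incision through 30 days post-procedure". SAP 4.2 defines it the same way. The derivation in SAP 7.9.3.1 counts subjects "who experience any related (device, procedure, or underlying condition/disease) adverse event prior to or during the 30 calendar-days post-procedure". It names no grade and no start point.

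**Readmission (endpoint 7).** Protocol 5.1.4 lists a rate through 30 days and says no more. SAP 7.9.3.1 begins: "A readmission in a subject is identified if a related (device, procedure, or underlying condition/disease) adverse event". It then requires onset on or after the procedure date and a hospital start date within 30 days.

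**Reoperation (endpoint 8).** The protocol again lists only a rate through 30 days. SAP 7.9.3.1 counts subjects "if they experience a related (device, procedure, or underlying condition/disease) adverse event that resulted in treatment with a surgical procedure". The only date used is the onset of the adverse event, with no lower bound.

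**Data available.** Protocol 12.1 collects adverse events to day 30 "regardless of their severity or relationship to the Hugo™ RAS or study procedures".

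**Role of the goals.** Protocol 14.5 and SAP 7.9.3 treat the secondary performance goals as benchmarks for interpretation. SAP 7.9.3.2 rules out hypothesis tests.

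**The concern.** A programmer will follow the derivation table, not the objectives section. For overall complications the table produces a different quantity from the one that both documents define. For readmission and reoperation it narrows a rate that a reader of the protocol would take as unqualified.

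Relatedness is a judgement made by people who know that the device was used, and a filter of this kind can only remove events. The rates are to be read against the goals in protocol 14.5. Protocol section 19 records, for version 8.0, that the complication-rate definition was changed to align with the literature behind those goals. The version 5.0 entry says that the secondary goals were added to help judge benefit and risk for marketing approval. A rate computed on another basis weakens that reading, and the report would contain no unrestricted rate to set beside it.

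**Working it through.** **1. The definitions side by side.**

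| Endpoint | Protocol 5.1.4 | SAP 7.9.3.1 | Difference |
|---|---|---|---|
| 1 Overall complications | Grade I or higher, first incision to day 30, any cause (SAP 4.2 agrees) | Related events, no grade, no start point | Contradiction, also within the SAP |
| 7 Readmission | Rate through 30 days, not defined further | Related events, onset on or after procedure date, hospital date within 30 days | Narrowing |
| 8 Reoperation | Rate through 30 days, not defined further | Related events, onset within 30 days, no start point, no operation date | Narrowing, with a looser window |

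Transfusion and mortality (endpoints 4 and 9) carry no relatedness condition, so the filter is not a general rule of the table.

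**2. How the filter is specified.** The primary safety derivation (SAP 7.9.2.2) names relatedness as adjudicated by the clinical events committee (CEC). Endpoints 1, 7 and 8 name no rater, although protocol Table 8 has both the investigator and the sponsor classify relatedness. SAP 7.9.3.5 says that any rating other than not related counts, but only for the exploratory analyses. The main analysis does not say whether a rating of possible counts.

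**3. Disclosure.** SAP 7.12 covers only the sensitivity analyses. The SAP history for version 3.0 mentions relatedness for the primary safety endpoint; for the secondary endpoints it mentions only the 30-day window.

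**4. The goals.** Two goals reproduce as the highest literature rate plus 10 points:
- nephrectomy readmission: 0.068 + 0.10 = 0.168 (stated 16.8%);
- prostatectomy reoperation: 0.156 + 0.10 = 0.256 (stated 25.6%).

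Neither source rate is described as all-cause or as related-only.

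**5. Size of the filter.** Let f be the share of subjects with an event whose events are all rated not related. The documents do not give f. I assume 5% to 20% to show the scale; at f = 0 there is no difference.

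The reported rate is the unrestricted rate × (1 − f), so the loss is rate × f. Taking the literature means in protocol 14.5 as unrestricted rates (also an assumption):
- nephrectomy complications, mean 0.116: loss 0.116 × 0.05 = 0.6 points to 0.116 × 0.20 = 2.3 points; the goal of 30% lies 18.4 points above the mean;
- nephrectomy readmission, mean 0.063: loss 0.3 to 1.3 points; the goal lies 16.8 − 6.3 = 10.5 points above the mean.

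A related-only rate exactly at its goal would correspond to an unrestricted rate of goal/(1 − f):
- nephrectomy complications: 0.30/0.95 = 31.6% to 0.30/0.80 = 37.5%;
- nephrectomy readmission: 0.168/0.95 = 17.7% to 0.168/0.80 = 21.0%;
- reoperation: 0.256/0.95 = 26.9% to 0.256/0.80 = 32.0%.

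For comparison, one subject is 1/55 = 1.8 points in the nephrectomy and prostatectomy groups and 1/31 = 3.2 points in the cystectomy group.

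**6. Direction.** The filter lowers all three rates. Leaving out the grade and start point (endpoint 1), and leaving out the start point and dating by onset (endpoint 8), can only raise them. The documents give no figures for these, so the net sign is unknown.

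**The case against.** Several points on the other side stand.

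- **The filter is wide.** "Underlying condition refers to a chronic disease or condition that a subject has prior to any acute treatment/surgery", so for most of these patients many events will qualify. Protocol 12.4 also classes unassessable cases as possible.
- **Part of the judgement is independent.** Under protocol 12.1 the CEC adjudicates deaths, serious events related to the system or procedure, and Grade III and IV complications. A reoperation is normally Grade III, so most will reach it. Grade I and II events, and lower-grade readmissions judged unrelated to the system and procedure, are not listed for it.
- **The start point appears elsewhere.** The protocol synopsis and 10.6 analyse adverse events from first incision, and SAP 4.2 repeats this for endpoint 1. The table still needs it, because collection begins at consent.
- **The missing grade changes little.** Grade I covers any deviation from the normal postoperative course.
- **The SAP may supply detail.** Protocol section 14 leaves technical detail to it, and 14.5 says that secondary endpoints explore effects tied to the procedure or the disease state. That gives some basis for a filter on endpoints 7 and 8. It does not cover endpoint 1, which both documents define.

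Three stronger readings are tempting but not supported.

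- **That all three endpoints contradict the protocol.** Only endpoint 1 does; the protocol gives no working definition of readmission or reoperation.
- **That all three are mismatched with their goals.** The version 8.0 note supports this for complications, and only as a statement of intent. For readmission and reoperation the documents do not say how the literature counted events, and the nephrectomy and cystectomy reoperation goals have no literature behind them.
- **That reclassifying one subject could decide a comparison.** For nephrectomy readmission, 9/55 = 16.4% is below 16.8% and 10/55 = 18.2% is above it. But nothing is decided by the comparison, and at the stated mean about 55 × 0.063 = 3.5 readmissions are expected. The binomial probability of 10 or more is about 0.2% (0.4% at 0.068).

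**Conclusion.** The point holds as a definitional conflict for overall complications, and as an undisclosed and under-specified narrowing for readmission and reoperation. Endpoint 8 also has a dating inconsistency, since endpoint 7 requires the hospital date to fall within 30 days and endpoint 8 requires no operation date.

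The numerical effect is probably small. Under the assumed 5% to 20% it is 0.6 to 2.3 points for nephrectomy complications at the literature mean, well short of the distance to the goal. A reader might infer that the SAP makes the device look safer overall. The documents do not show that, because the filter and the loose windows pull in opposite directions.

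Sample size, alpha, power and the success criterion do not depend on these endpoints. The point is worth correcting because the table as written will not produce the endpoint that the protocol names, and because the correction is cheap.

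**What to change.** In SAP 7.9.3.1:

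1. **Endpoint 1:** any adverse event of Clavien-Dindo Grade I or higher with onset from first incision through day 30, with no relatedness condition.
2. **Endpoints 7 and 8:** all-cause rates from first incision through day 30. Keep the hospital date for readmission, and date reoperation by the operation where that date is recorded.
3. **Related-only rates as supportive.** SAP 7.9.3.5 already plans these by cause for endpoint 1; they need to be added for endpoints 7 and 8.
4. **Relatedness:** name whose rating is used and which ratings count as related.

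If the sponsor prefers related-only as the main analysis, the protocol should be amended to say so, with the literature definition behind each goal stated.

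**Cost.** For endpoint 1 this is SAP wording, since all adverse events to day 30 are collected. For endpoints 7 and 8, protocol Table 6 schedules both items, but the documents do not show that an operation date, or a readmission not arising from an adverse event, is recorded; the case report form should be checked. The reported rates may be slightly less favourable.

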Complication	
Complications will be defined according to the Clavien-Dindo classification system.¹
 
Grade I: Any deviation from the normal postoperative course without the need for pharmacological treatment or surgical, endoscopic, and radiological interventions. Allowed therapeutic regimens are: drugs as antiemetics, antipyretics, analgetics, diuretics, electrolytes, and physiotherapy. This grade also includes wound infections opened at the bedside.
 
Grade II: Requiring pharmacological treatment with drugs other than such allowed for grade I complications. Blood transfusions and total parenteral nutrition are also included.
 
Grade III: Requiring surgical, endoscopic, or radiological intervention
 
Grade IIIa: Intervention not under general anesthesia
 
Grade IIIb: Intervention under general anesthesia
 
Grade IV: Life-threatening complication (including CNS complications)* requiring IC/ICU management
 
Grade IVa: Single organ dysfunction (including dialysis)
 
Grade IVb: Multiorgan dysfunction
 
Grade V: Death of a patient

Medtronic Business Restricted

This document is electronically controlled

CONFIDENTIAL 056-F275 Rev E Clinical Investigation Plan Template

	
NOTE 1: If the patient suffers from a complication at the time of discharge (see examples in Appendix 18.1), the suffix "d" (for "disability") is added to the respective grade of complication. This label indicates the need for a follow-up to fully evaluate the complication.
 
NOTE 2: *Brain hemorrhage, ischemic stroke, subarachnoidal bleeding, but excluding transient ischemic attacks. CNS, central nervous system; IC, intermediate care; ICU, intensive care unit.

Other	

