14.5 Secondary Objectives

The secondary objective of this study is to demonstrate the Medtronic Hugo™ RAS System performs as intended when used in urologic robotic assisted surgery. The secondary endpoints of this study will assess the overall performance of the Medtronic Hugo™ RAS System when used for urologic robotic surgery.

The following short-term secondary endpoints will be assessed:

Medtronic Business Restricted

This document is electronically controlled

CONFIDENTIAL 056-F275 Rev E Clinical Investigation Plan Template

- Complication rate: Overall rate of subjects with one or more major complications (Clavien-Dindo Grade I or higher), from the first incision through 30 days post-procedure
- Operative time
- Intraoperative estimated blood loss (mL)
- Transfusion rate
- Rate of device-related conversion
- Hospital length of stay
- Readmission rate (through 30 days)
- Reoperation rate (through 30 days)
- Mortality rate (through 30 days)
- Rate of device deficiencies

The following long-term secondary endpoints will be assessed through 5 years in oncologic subjects:

- Overall survival
- Progression-free survival
- Disease-free survival

Descriptive statistics will be used to summarize secondary endpoints. In addition, performance goals are pre-specified based on meta-analysis of published study data as well as considerations of clinically meaningful margins and statistical confidences for most secondary endpoints (see details below; the full bibliography of 130 publications supporting the updated performance goals is included in **Section 17.1**). 95% confidence intervals might be provided as appropriate. Statistical evaluations for secondary objectives with performance goals are not powered in this study. Additionally, the secondary endpoints are planned to be analyzed using descriptive statistics, which broadly negate the need for multiplicity adjustments.

The role of the secondary endpoints is to explore additional effects and outcomes associated with either the procedure or the disease state. The pre-specified performance goals serve as benchmarks for interpretation rather than thresholds for statistical significance of clinical trial success in this study.

Performance Goals for Secondary Endpoints

Performance goals are specified for each of the secondary endpoints. The details are summarized in the following table.

Medtronic Expand URO Clinical Investigation Plan

MDT19051EINURO

Version 9.0

Page 73 of 111

Medtronic

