	Cystectomy	500 mL	The mean effect size is 133.0 with a 95% confidence interval of 102.6 to 163.4. The 95% prediction interval was not able to be obtained due to a lack of data. As there are few literature cohorts available for this endpoint, the performance goals of the other two surgical cohorts were considered in setting this endpoint's performance goal of 500.
Transfusion rate	Nephrectomy	30%	The mean effect size is 0.079 with a 95% confidence interval of 0.056 to 0.11. The 95% prediction interval is 0.021 to 0.257. A performance goal of 0.30 is clinically appropriate for descriptive comparison.
	Prostatectomy	60%	The mean effect size is 0.020 with a 95% confidence interval of 0.011 to 0.037. The 95% prediction interval is 0 to 0.534. A performance goal of 0.60 is clinically appropriate for descriptive comparison.
	Cystectomy	55%	The mean effect size is 0.133 with a 95% confidence interval of 0.050 to 0.308. The 95% prediction interval is 0.004 to 0.869. While below the 95% prediction interval upper limit, a performance goal of 0.550 is better aligned for a descriptive comparison.
Rate of device-related conversion	Nephrectomy	15%	The literature search failed to identify studies that reported on device-related conversions. Device related conversions are expected to be a fraction of the total conversions. Conversion Rate = 100% - Surgical Success Rate, which has a performance goal of 85%. Thus, a 15% performance goal is assumed for conversions.
	Prostatectomy	15%	The literature search failed to identify studies that reported on device-related conversions. Device related conversions are expected to be a fraction of the total conversions. Conversion Rate = 100% - Surgical Success Rate, which has a performance goal of 85%. Thus, a 15% performance goal is assumed for conversions.
	Cystectomy	15%	The literature search failed to identify studies that reported on device-related conversions. Device related conversions are expected to be a fraction of the total conversions. Conversion Rate = 100% - Surgical Success Rate, which has a performance goal of 85%. Thus, a 15% performance goal is assumed for conversions.

Medtronic Business Restricted

This document is electronically controlled

CONFIDENTIAL 056-F275 Rev E Clinical Investigation Plan Template

Medtronic Expand URO Clinical Investigation Plan

MDT19051EINURO

Version 9.0

Page 75 of 111

Medtronic

Endpoint	Procedure Type	PG	Rationale

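### The transfusion endpoint counts only transfusions tied to an adverse event and a bleeding complication, so it is likely to fall below the unqualified rate it is compared with

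*SAP*

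**What the plan says.** **Endpoint.** Protocol 5.1.4 and 14.5 and SAP 4.2 list a transfusion rate with no qualifier. Protocol 6.4.2 names transfusions among the measures meant to give a full picture of device safety.

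**Collection.** Protocol Table 6 schedules transfusion at Visits 2, 2.1 and 3. Its footnote 3 restricts the item to transfusions linked to an AE. Estimated blood loss, in the same table, has no such restriction.

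**Counting.** SAP 7.9.3.1, endpoint 4, begins: "Occurrence of a blood transfusion is captured as an adverse event". The next sentence sets the rule: "A blood transfusion is defined as an AE that resulted in any treatment and then a bleeding complication led to a blood transfusion". It then adds a limit of 30 calendar days after the procedure.

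**Comparator.** Protocol 14.5 states that "performance goals are pre-specified based on meta-analysis of published study data". The transfusion rows give:
- nephrectomy, goal 30%: "The mean effect size is 0.079 with a 95% confidence interval of 0.056 to 0.11"
- prostatectomy, goal 60%: "The mean effect size is 0.020 with a 95% confidence interval of 0.011 to 0.037"
- cystectomy, goal 55%: "The mean effect size is 0.133 with a 95% confidence interval of 0.050 to 0.308"

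None of these rows mentions an AE or bleeding condition.

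**Grading.** Under Clavien-Dindo Grade II, protocol Table 7 says: "Blood transfusions and total parenteral nutrition are also included".

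**Role.** SAP 7.9.3 says: "The pre-specified performance goals serve as benchmarks for interpretation rather than thresholds for statistical significance of clinical trial success in this study".

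**The concern.** The endpoint's name and its benchmark refer to transfusions. What is tabulated is a subset that passes two filters: the transfusion must be linked to an AE, and a bleeding complication must have led to it. The result then depends partly on how a site attributes a transfusion, and not only on whether blood was given. Any error runs one way, towards a lower and more favourable rate.

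The SAP sentence is also hard to parse. It joins an AE that led to some treatment with a later bleeding complication, and two programmers could derive different counts from it.

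At stake is a descriptive safety rate that readers will set beside published figures. A benchmark helps interpretation only if both sides measure the same thing.

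**Working it through.** **1. Which transfusions reach the count, taking the rules as written**

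| Situation | Collected (Table 6, footnote 3) | Counted (SAP endpoint 4) |
|---|---|---|
| Bleeding AE leading to transfusion | Yes | Yes |
| Non-bleeding AE (e.g. anaemia) with transfusion | Yes | No |
| Intraoperative transfusion, no AE reported | Not required | No |

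The counted events are a subset of all transfusions, so counted rate ≤ all-transfusion rate. Equality holds only if the second and third rows are empty.

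**2. Expected numbers if every transfusion counted**

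Inputs are the literature means and goals in protocol 14.5 and the maximum cohort sizes in protocol 14.7. The pooled means cannot be recomputed, because the study-level data are not in the documents. Expected count = mean × n; goal count = goal × n.

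| Procedure | Mean × n | Goal × n | Largest whole count at or below goal |
|---|---|---|---|
| Nephrectomy | 0.079 × 55 = 4.3 | 0.30 × 55 = 16.5 | 16 |
| Prostatectomy | 0.020 × 55 = 1.1 | 0.60 × 55 = 33.0 | 33 |
| Cystectomy | 0.133 × 31 = 4.1 | 0.55 × 31 = 17.05 | 17 |

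Full capture at the literature means would leave every cohort far below its goal.

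**3. Illustrative effect on the reported rate**

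Reported rate = true rate × capture fraction. The documents give no capture fraction, so the values below are assumptions that only show sensitivity. The true rate is set at the literature mean.

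| Procedure | 100% | 75% | 50% | 25% |
|---|---|---|---|---|
| Nephrectomy | 7.9% | 5.9% | 4.0% | 2.0% |
| Prostatectomy | 2.0% | 1.5% | 1.0% | 0.5% |
| Cystectomy | 13.3% | 10.0% | 6.7% | 3.3% |

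**4. Capture below which the expected rate leaves the literature confidence interval**

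Threshold = lower confidence limit ÷ mean.
- Nephrectomy: 0.056 / 0.079 = 71%
- Prostatectomy: 0.011 / 0.020 = 55%
- Cystectomy: 0.050 / 0.133 = 38%

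For nephrectomy, losing somewhat under a third of events would place an average device below the literature interval through ascertainment alone.

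**5. Sampling error for scale**

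Exact 95% intervals are 2.0% to 17.6% for 4 of 55 and 0.4% to 12.5% for 2 of 55. For cystectomy they are 3.6% to 29.8% for 4 of 31 and 0.8% to 21.4% for 2 of 31. Halving the count shifts the estimate, but the intervals still overlap widely.

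**The case against.** The strongest defence is that most transfusions should reach the AE form anyway. Transfusion is a Grade II complication. Protocol 12.1 collects all AEs through 30 (+7) days whatever their severity or relatedness. The AE definition in Table 7 includes abnormal laboratory findings, and neither anaemia nor transfusion is among the unavoidable events exempted in Table 9. The SAP's opening sentence can also be read as making every transfusion an AE, and the awkward second sentence may only describe how the form branches.

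Much of this stands. A reader might infer that a ward transfusion for anaemia is never recorded; the reporting rules do not support that, because such an event appears reportable and footnote 3 would then admit the transfusion. A reader might also infer that missed transfusions depress the any-complication rate. That would require a site not to report a Grade II event and the subject to have no other related AE, and the documents show neither.

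The defence does not remove the bleeding condition, which on its wording excludes the anaemia case at the counting step. Nor does it settle intraoperative transfusion for expected loss, because Grade I is framed as deviation from the postoperative course. If every transfusion is meant to be an AE, footnote 3 has no function.

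A second defence is that secondary endpoints are descriptive and untested (SAP 7.9.3.2). That is correct and limits the consequence. It does not make a subset comparable with an unqualified rate.

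**Conclusion.** The point holds in a limited form. As written, the rules omit recorded transfusions tied to a non-bleeding AE and may miss intraoperative transfusions with no AE. The direction is certain: the rate cannot exceed the all-transfusion rate. An undercount is likely but not established. Its size is unknown and could be small or nil.

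The comparison with the literature rests on one further assumption, that the source publications counted transfusions without these filters. The plain label and the goal rows suggest so, but the documents do not give the source definitions. If some publications counted only transfusions reported as complications, the mismatch shrinks.

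A reader might infer that the filters let the device meet its transfusion goals. The figures do not support that: about 4.3, 1.1 and 4.1 expected subjects stand against goal counts of about 16, 33 and 17. Study success rests on the primary endpoints (protocol 14.1) and is unaffected. What is affected is the reported rate and its reading against the literature.

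**What to change.** **SAP.** Redefine endpoint 4 as any blood transfusion from first incision through 30 calendar days. Drop the bleeding-complication condition and report the bleeding-related subset as a sub-row.

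**Protocol and eCRF.** At the next revision, delete footnote 3 and record every transfusion (yes/no, date) at Visits 2, 2.1 and 3, regardless of AE status. The SAP change alone cannot recover transfusions that were never collected.

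**Subjects already treated.** Where permitted, complete the field from existing hospital records, which protocol 10.7 accepts as source documents, for the period before study exit. Protocol 10.9.1 stops collection of study data after exit, so the back-fill must respect that limit. Where it is not possible, state in the report that the rate covers AE-linked transfusions only and is not directly comparable with the goals.

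**Cost.** One field, a short chart check, and protocol and SAP wording. The protocol change needs FDA and IRB approval before use (protocol 16.6). The reported rate may rise.
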